6. GENERAL ASPECTS FOR STATISTICAL ANALYSIS

6.1. STATISTICAL NOTATION AND METHODOLOGY

Unless otherwise stated, the term "descriptive statistics" refers to the number of subjects (n), mean, median, standard deviation, minimum, and maximum for continuous variables and frequencies and percentages for categorical variables.

Unless specified otherwise, the denominator for percentages for categorical data will be based on the number of subjects or observations with non-missing data appropriate for summary purposes. The denominator for percentages for incidence data (such as AEs) will be based on the number of subjects in the analysis population "at risk". Select ordinal data may be summarized using both descriptive statistics and counts and percentages of subjects in each category, as appropriate.

Minimum and maximum values will be presented at the precision of the original value, means and medians will be rounded to 1 decimal place greater than the precision of the original value, standard deviations and standard errors will be rounded to 2 decimal places greater than the precision of the original value. Percentages will be rounded to 1 decimal place. Percentages that round down to 0 or up to 100% will be displayed as "<0.1%" and ">99.9%", respectively. Other statistics (e.g., confidence intervals [CIs]) will be presented using the same general rules outlined above or assessed for the most appropriate presentation based on the underlying data.

Unless otherwise noted, values reported as greater than or less than some quantifiable limit (e.g., "< 1.0") will be summarized with the sign suppressed in summary tables and figures, using the numeric value reported. Data will display on subject listings to include the sign.

In general, summary tables will be presented by combining subjects from each of the treatment pathways into a single treatment group (AR101).

All relevant data collected in the database and any derived data will be included in data listings and unless otherwise noted sorted by treatment pathway, subject ID, test/measurement, and visit and time point as appropriate.

All statistical methods will be based on the International Conference on Harmonisation (ICH)-E9 Guidance for Industry "Statistical Principles for Clinical Trials".

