9.1. ADVERSE EVENTS

TEAEs will be summarized excluding symptoms recorded during the food challenges.

AEs will be classified by severity using the Consortium of Food Allergy Research (CoFAR) grading system for allergic reactions, modified European Academy of Allergy and Clinical Immunology (EAACI) guidelines for anaphylactic reactions, and Common Terminology Criteria for Adverse Events (CTCAE) for all other AEs, all as per Section 8.2.2.1 of the protocol.

If symptoms are recorded as part of an anaphylactic reaction, only the single anaphylactic reaction event will be summarized and not the individual symptoms.

All reported AEs will be classified into SOC and PT using MedDRA version 26.0.

TEAEs are defined as those AEs with onset after the first dose of AR101 in ARC008 and no more than 30 days after the last dose of study drug. Non-TEAEs will be listed by treatment pathway and subject ID; these events will not be summarized. TEAEs will be summarized for the Safety Population by study period as follows:

- Initial Escalation
- Up-Dosing
- Initial and Extended Maintenance
- Overall (Initial Escalation, Up-Dosing, and Initial and Extended Maintenance)

Summaries that are displayed by system organ class and preferred terms will be ordered by descending incidence of system organ class and preferred term within each system organ class. Summaries displayed by preferred term only will be ordered by descending incidence of preferred term. Summaries of the following types will be presented:

• Overall summary of the number of unique TEAEs and TESAEs and subject incidence of TEAEs and TESAEs meeting various criteria;

- Overall summary of the number of unique TEAEs and TESAEs and subject incidence of TEAEs and TESAEs meeting various criteria by total exposure including parent studies;
- Subject incidence of TEAEs by MedDRA system organ class and preferred term;
- Subject incidence of TEAEs by severity grade, MedDRA system organ class, and preferred term;
- Subject incidence of grade ≥ 3 severity TEAEs by MedDRA system organ class and preferred term;
- Subject incidence of TESAEs by MedDRA system organ class and preferred term;
- Subject incidence of TEAEs leading to discontinuation of study product by MedDRA system organ class and preferred term;
- Subject incidence of TEAEs leading to discontinuation of study product by total AR101 exposure including parent studies, MedDRA system organ class, and preferred term;

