- Subject incidence of treatment-related AEs by MedDRA system organ class, and preferred term;
- Subject incidence of grade ≥ 3 severity treatment-related AEs by MedDRA system organ class and preferred term;
- Subject incidence of treatment-related AEs leading to discontinuation of study product by MedDRA system organ class and preferred term;
- Subject incidence of TEAEs associated with epinephrine use by MedDRA system organ class and preferred term; and
- Subject incidence of TEAEs associated with accidental/non-accidental non-study product food allergen exposure by MedDRA system organ class and preferred term.

The overall summary of TEAEs and TESAEs will be repeated for the subgroups described in Section 6.3.

At each level of summarization (e.g., any AE, SOC, and PT), subjects experiencing more than one TEAE will be counted only once within each study period. In the summary of TEAEs by severity grade, subjects will be counted once at the highest severity reported at each level of summarization.

AE data will be presented in data listings by treatment pathway, subject ID, and event date. TEAEs for subjects who did not tolerate non-daily dosing in Treatment Pathway 1 and switched to Treatment Pathway 2 will be presented in the data listings. Non-TEAEs, TEAEs, TEAEs identified as the primary reason for early study product discontinuation, TEAEs identified as the primary reason for early study discontinuation, treatment-emergent GI AEs in subjects who discontinued treatment due to GI AEs and had follow-up due to recurrent GI symptoms, treatment-emergent allergic AEs excluding food allergens, and treatment-emergent allergic AEs caused by food allergens will also be presented in separate data listings.

A listing of deaths will also be presented.

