9.2.1. Anaphylaxis

Anaphylactic AEs will be considered AEIs. Anaphylaxis is defined by a number of signs and symptoms that occur alone or in combination within minutes up to a few hours after exposure to a provoking agent. The severity of the reaction will be assessed according to the EAACI system for grading the severity of anaphylactic reactions (Muraro, 2007).

All reported anaphylactic reaction episodes will be listed by treatment pathway and subject.

Each anaphylactic reaction will be identified by the following triggers:

• Study product/Investigational product (IP)

- Peanut or peanut-containing food
- Other food allergen
- Medication
- Insect sting
- Environmental allergen(s)
- Other
- Unknown

Treatment-emergent anaphylactic reactions include anaphylactic reactions that occur after first dose of AR101 in ARC008 through 30 days after last dose of study product, but excluding anaphylactic reactions that occur during or related to a food challenge. Treatment-emergent anaphylactic reactions will be summarized in the Safety Population separately for the following study periods:

- Initial Escalation
- Up-Dosing
- Initial and Extended Maintenance
- Overall (Initial Escalation, Up-Dosing, and Initial and Extended Maintenance)

Summaries of each study period will include:

- The number of anaphylactic reactions.
- The number of anaphylactic reactions by trigger, study product, peanut or peanutcontaining food, other food allergen, medication, insect sting, environmental allergen, other and unknown.
- Incidence of subjects experiencing an anaphylactic reaction by number of episodes, subjects experiencing an anaphylactic reaction by severity using modified EAACI guidelines, subjects experiencing an anaphylactic reaction that was a SAE, subjects experiencing an anaphylactic reaction that required epinephrine use, the location of epinephrine episodes (home or study site), and the individual symptoms involved.

The above summary will be produced for all treatment-emergent anaphylactic reactions, all treatment-emergent anaphylactic reactions by total AR101 exposure including parent studies, and for treatment-related anaphylactic reactions. Anaphylactic reactions will also be listed by treatment pathway, subject ID, and episode date.

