9.11. STUDY TREATMENT EXPOSURE

The calculation of exposure will be based on in clinic dosing data and at home dosing as captured on the Study Product Exposure CRF page.

First and last dose dates for each study period are identified as described in Section 7.5.

The total amount of study product consumed will be calculated as the sum of in-clinic doses plus the estimated number of doses taken at home. At-home doses will be estimated by combining the doses across each dosing interval entered on the Study Product Exposure CRF page and taking into account the dosing frequency and any missed and partial doses as captured on the Subject Dosing Diary CRF.

The following calculations of study drug exposure will be made and summarized:

• Duration of Exposure (in days and in years): calculated as the date of last dose of study drug minus the date of the first dose of AR101 plus one during the study

> period, except for the Initial Escalation period, where the duration of exposure will only be 1 or 2 days depending on whether drug was taken on Initial Escalation Day 1 and Initial Escalation Day 2. Duration of exposure will be summarized using descriptive statistics for continuous data as well as categorically by 28-day increments for the first year and by year for the overall treatment periods: \leq 28 days, 29 to 56 days, 57 to 84 days, ..., 1 to < 2 years, 2 to < 3 years, 3 to < 4 years, 4 to < 5 years, and \geq 5 years.

- Total dose consumed (mg): calculated as the cumulative sum of all doses taken during the study period.
- Average dose per day (mg): calculated as the total dose consumed divided by the number of days during the study period.
- Maximum dose achieved (mg/day): summarized using descriptive statistics for continuous data as well as categorically using all possible dose levels: 0.5, 1, 1.5, 3, 6, 12, 20, 40, 80, 120, 160, 200, 240, or 300 mg/day.
- Number of unsuccessful dose increases: calculated as the number of single doses given at the study site at a higher dose level followed by an immediate return to the previous dose level or a lower dose level.
- Number of dose reductions: calculated as the number of any decrease in dose level given at the study site that does not qualify as an unsuccessful dose increase.

Study treatment exposure parameters will be summarized by the following study periods:

- Initial Escalation
- Up-Dosing
- Initial and Extended Maintenance

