- Overall (ARC008 Only: Initial Escalation, Up-Dosing, and Initial and Extended Maintenance)

Duration of exposure will also be summarized including parent studies (Overall [Including Parent Studies]).

All ARC008 exposure data from the Dose Administration, Study Product Exposure, Missed and Partial Doses Log, and Subject Dosing Diary CRFs will be included in the subject listings.

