Prior medications, concomitant medications, and rescue medications will be summarized separately by ATC Class and generic drug name. Summaries of prior and concomitant medications will include medications from parent studies (ARC002, ARC003, ARC004, ARC005, ARC007, ARC010, and ARC011). Subjects will be counted no more than one time per generic drug name and no more than one time per ATC Level 4.

Rescue medications will be summarized by ATC Class and generic drug for the following study periods:

• Initial Escalation

- Up-Dosing
- Initial and Extended Maintenance (excluding rescue medications taken as a result of an OLFC)
- OLFCs (Total AR101 Exposure < 1 year; 1 to < 2 years; 2 to < 3 years; 3 to < 4 years; 4 to < 5 years; ≥ 5 years)
- DBPCFCs (Total AR101 Exposure < 1 year; 1 to < 2 years; 2 to < 3 years; 3 to < 4 years; 4 to < 5 years; ≥ 5 years)
- Overall, including all rescue medications reported on the CRF

The summary of rescue medications will be repeated for the subgroups described in Section 6.3.

Prior medications and concomitant medications (including medications from parent studies [ARC001, ARC002, ARC003, ARC004, ARC005, ARC007, ARC010, and ARC011]), prior and on-study rescue medications, prior and on-study epinephrine, and concomitant non-drug therapies will be listed by subject.

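### The adverse event tables by total AR101 exposure give crude incidence over bands with unequal ARC008 time at risk, and plan no person-time

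*SAP*

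**What the plan says.** SAP 9.1 lists an overall TEAE and TESAE summary by total exposure including parent studies, and "Subject incidence of TEAEs leading to discontinuation of study product by total AR101 exposure including parent studies". SAP 9.2.1 adds a table of "all treatment-emergent anaphylactic reactions by total AR101 exposure including parent studies". All three are event counts and subject incidence.

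TEAEs are events "with onset after the first dose of AR101 in ARC008 and no more than 30 days after the last dose of study drug". Parent-study time therefore counts towards exposure but not towards the period in which events are counted.

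The rules nearest to an allocation rule are these:

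- SAP 6.1 sets the incidence denominator as "based on the number of subjects in the analysis population" at risk, without defining at risk for exposure bands.
- SAP 9.1 says that "subjects experiencing more than one TEAE will be counted only once within each study period". It does not mention exposure bands.
- SAP 9.11 gives yearly cut points ("1 to < 2 years, 2 to < 3 years, 3 to < 4 years, 4 to < 5 years") for duration of exposure only, and adds that "Duration of exposure will also be summarized including parent studies". Neither is tied to events.
- SAP 9.12 uses exposure bands ("Total AR101 Exposure < 1 year; 1 to < 2 years; 2 to < 3 years; 3 to < 4 years" and beyond) for rescue medication at food challenges.

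SAP 18 leaves the planned outputs to a shell document that is not among the papers supplied.

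**The concern.** The primary objective is to describe safety during longer-term administration. The study-period tables in SAP 9.1 treat Initial and Extended Maintenance as one period. In the SAP text, the three by-exposure tables are therefore the only adverse event summaries that can show how risk moves with years of treatment.

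A crude percentage per band answers that question only if subjects in each band are observed for similar lengths of time. Here they are not. Former-placebo subjects enter ARC008 with no AR101 exposure, and others enter with months or years already accrued. SAP 2.4.2.6 then ends treatment at about 3 or about 5 years in total, or earlier for certain US subjects. Differences between bands will partly reflect observation time, whichever way subjects and events are placed. A reader could take such a pattern for accumulating risk or for improving tolerability.

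**Working it through.** The documents give no event rate, so there is no planned figure to reproduce. The check holds the true rates constant, so that any trend across bands is an artefact of the tabulation.

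**Inputs from the documents**
- ARC005 share: 132/950 = 13.9% (Protocol 1.2.5 and 3.5), randomised 2:1. This is an upper bound, because it assumes that every randomised subject rolls over.
- Stops at about 3 years in total for ARC005 and about 5 years for others (SAP 2.4.2.6).
- Prior exposure of continuing non-ARC005 subjects: from 22 + 12 = 34 weeks (0.65 y) to 52 + 24 + 84 = 160 weeks (3.1 y). Up-dosing length is taken from Pathway 3 (Protocol 3.2.3.2), and maintenance lengths from Protocol 1.2.2 and 1.2.4.

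**Assumptions, not in the documents**
- Any TEAE 0.2 per person-year (PY); AE-discontinuation 3 per 100 PY; other stopping 10 per 100 PY.
- 30% of non-ARC005 subjects are former placebo with zero prior exposure; the rest are spread uniformly over 0.65-3.1 y. ARC005 subjects have 1 y prior exposure if treated, otherwise 0.
- Actual stop at 3-3.5 y for ARC005 and at 5-5.5 y (or 5-7 y) for others.
- US commercial-access stops and the 30-day post-dose tail are not modelled.

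**Any TEAE, % of subjects (simulation, 2,000,000 subjects)**

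| Total exposure | By final exposure | By exposure at onset, among those at risk |
|---|---|---|
| <1 y | 8.8 | 14.0 |
| 1-<2 y | 16.7 | 14.2 |
| 2-<3 y | 24.4 | 14.8 |
| 3-<4 y | 36.2 | 15.4 |
| 4-<5 y | 44.2 | 17.0 |
| ≥5 y | 52.1 | 4.7 (16.2 with stops at 5-7 y) |

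Events per PY are 0.20 in every band.

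**Hand checks**
- Final exposure: incidence p corresponds to −ln(1−p)/0.2 years at risk. That is −ln(0.912)/0.2 = 0.46 y in the first band and −ln(0.479)/0.2 = 3.7 y in the last. The rise is time at risk and nothing else.
- Onset: a full year in a band gives 1 − exp(−0.2) = 18.1%. With stops uniform over 5-5.5 y, mean time in the last band is about 0.25 y, giving 1 − exp(−0.05) = 4.9%, or 4.7% after attrition.

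**Sensitivity to the assumed rate (final exposure, first to last band, across stopping scenarios)**
- 0.05/PY: 2-3% to 17-20%.
- 0.2/PY: 9-11% to 52-58%.
- 1/PY: 35-43% to 96-98%.

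**AE-discontinuation**
- By final exposure at constant hazards, the proportion is 3/(3 + 10) = 23.1% in any band without administrative endings. It is flat, and falls only where planned or early stops add subjects to a band.
- By exposure at onset it is 2.3-2.8% per band below 5 y in this scenario and 0.7% at ≥5 y with 5-5.5 y stops.
- The person-time rate stays at about 3 per 100 PY throughout.

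**A declining risk can look like a rising one.** A separate run assumed that 35% of subjects enter at 0 y and 65% at 1.5 y, that treatment ends at 5 y, and that the exit hazard is 0.12/y. Anaphylaxis was set to fall from 20 to 3 per 100 PY. Incidence by final exposure still rose, from 9.1% to 25.5%.

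**The case against.** The strongest reply is that the large figures belong to one reading only. A reader might infer that the SAP will class subjects by final exposure. The text does not say so. The at-risk denominator in 6.1 and the listing of exposure bands among the study periods in 9.12 fit exposure at onset at least as well, and the shells may settle it. Under the onset reading, distortion below 5 years is modest. This stands, and it limits the size of the point. It does not remove the point, because the ≥5 y band still depends on how soon subjects stop after 5 years.

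A reader might also infer that AE-discontinuation will show a false decline with exposure. The documents do not establish that. At constant hazards it is flat by final exposure, and any dip depends on where administrative stops fall. SAP 2.4.2.6 also ends treatment for US subjects from ARC007 and ARC011 with commercial access, and permits it for US subjects from ARC002 and ARC004. These stops are not modelled, and ARC007 alone randomised 506 subjects in the US and Canada, so one cannot say that most subjects stop at 5 years. The ARC005 stop also requires commercial availability in the subject's country.

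The flat rates are a device. Protocol 1.1 reports that dosing symptoms in earlier immunotherapy studies tended to lessen over time.

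Finally, the study is descriptive, and SAP 9.11 summarises exposure duration. Overall exposure time could be recovered from that, but not by band and not restricted to the ARC008 time in which events count. A descriptive percentage still needs comparable time at risk if bands are read against each other.

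**Conclusion.** The point holds as a cheap improvement to the three by-exposure tables. Missing cut points and allocation wording alone would be a matter of detail. The substance is that crude incidence misleads when bands differ in ARC008 time at risk, which can happen under either reading, and no person-time is planned to correct it.

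Under the stated assumptions, a constant TEAE rate appears as a rise from about 9% to 52% by final exposure. By exposure at onset it appears as 14-17% followed by 4.7% (16% with later stops). The direction follows from the unequal time at risk. The sizes rest on assumed rates, assumed prior exposure and a simplified set of stop rules, and do not predict what the study report will show.

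**What to change.** In the by-exposure tables of SAP 9.1 and 9.2.1:

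- Use the yearly bands already given in 9.11 and 9.12.
- Assign each event to the total exposure reached at onset, and state this in a footnote. If the shells already fix the allocation, report that rule.
- Beside subject incidence, give the number of events per 100 ARC008 person-years at risk in the band, with delayed entry at the first ARC008 dose.
- Count time to 30 days after the last dose for TEAEs and anaphylaxis, matching the event window. For AE-discontinuation, stop at the last dose, because it cannot occur afterwards.
- Do not show the trend over years with a first-event rate censored at that event. If subjects differ in susceptibility, it falls artificially. With constant individual rates averaging 1/PY, gamma frailty of shape 1 and 30% early endings (all assumed), it drops from 0.74 to 0.24/PY across the bands.
- If former-placebo subjects (Pathways 3 and 5) are shown separately, keep Pathway 2 apart from Pathways 1 and 4, because it includes up-dosing.
- Label the rates post hoc. SAP 6.1 allows additional analyses on those terms, and SAP 1.1 shows that the database is already locked.

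The cost is extra programming and footnotes. Dose dates, onset dates and parent-study exposure are already needed for the planned tables. Some cells will be small. Later bands still contain selected subjects who stayed on treatment, so the rates remain descriptive.

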9.2. ADVERSE EVENTS OF INTEREST

AEIs include anaphylaxis, GI AEs with prolonged dose interruption (> 7 consecutive days) or that result in early discontinuation, accidental and non-accidental food allergen exposure, severe AEs, and use of epinephrine. Allergic reactions during food challenges will not be considered related to study product or reported as AEIs.

A separate data listing and an overall summary of the number of unique treatmentemergent AEIs and treatment-emergent serious AEIs and subject incidence of treatmentemergent AEIs and treatment-emergent serious AEIs meeting various criteria will be presented for the following AEIs: GI AEs leading to disruption of dosing (with prolonged dose interruption > 7 consecutive days or leading to treatment discontinuation), AEs associated with epinephrine use (excluding use for food allergen exposure or food challenges) or anaphylactic reactions (excluding food challenges unless the reaction was serious), serious treatment-related AEs, treatment-related AEs leading to study product discontinuation, and treatment-related AEs that are severe, life-threatening, or fatal.

The overall summary of treatment-emergent AEIs and treatment-emergent serious AEIs will be repeated for the subgroups described in Section 6.3.

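### SAP 9.2 excludes food-challenge reactions from adverse events of interest, then readmits serious anaphylaxis, so its summary and the 9.2.1 anaphylaxis summary follow different rules

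*SAP*

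**What the plan says.** Frequency of anaphylaxis is one of the primary safety endpoints (SAP 3.1). Four SAP statements and two protocol statements govern how anaphylaxis at a food challenge is reported.

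- SAP 9.2, first paragraph: "Allergic reactions during food challenges will not be considered related to study product or reported as AEIs". Protocol 8.1.4 has the same rule. Neither makes an exception for serious reactions.
- SAP 9.2, second paragraph: the AEI listing and overall AEI summary take in "anaphylactic reactions (excluding food challenges unless the reaction was serious".
- SAP 9.2.1: treatment-emergent anaphylactic reactions, the basis of the anaphylaxis summary, are defined "but excluding anaphylactic reactions that occur during or related to a food challenge". One line of that summary is "subjects experiencing an anaphylactic reaction that was a SAE". Separately, "All reported anaphylactic reaction episodes will be listed by treatment pathway and subject".
- SAP 9.1: "TEAEs will be summarized excluding symptoms recorded during the food challenges".
- Protocol 8.3: an allergic reaction at a challenge that meets the seriousness criteria is reported as related to the procedure. It is not said to be an AEI.

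**The concern.** Within SAP 9.2, one paragraph shuts out all challenge reactions and the next lets the serious ones in. The readmitting clause also disagrees with protocol 8.1.4 and with SAP 9.2.1. A programmer following each section literally would build two safety outputs on different rules for the same event.

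At stake is whether the AEI summary and the anaphylaxis summary can be read against each other. The plan reports serious AEIs as such and repeats the AEI summary for Treatment Pathways 1-3 and 4-5 (SAP 6.3). A reader who finds a serious anaphylactic reaction in one table and not in the other has nothing in the plan to explain it. Challenges are a plausible source of such events: the top challenge dose is 2000 mg (4043 mg cumulative), and protocol 1.4.1.2 warns that challenge reactions can be severe.

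**Working it through.** The point rests on no figure and the plan states none to reproduce, so the check is to trace particular events through each rule.

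Two timing facts set the scope. The treatment-emergent window runs from after the first ARC008 dose to "no more than 30 days after the last dose of study drug" (SAP 9.1; 9.2.1 uses the same 30 days). The Study Exit visit, with its optional double-blind challenge, is about 12 months after the last dose (SAP 2.4.2.8).

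| Anaphylactic reaction | SAP 9.2 first paragraph and protocol 8.1.4 | AEI summary, SAP 9.2 second paragraph | Anaphylaxis summary, SAP 9.2.1 | Anaphylaxis listing, SAP 9.2.1 |
|---|---|---|---|---|
| Serious, at an on-treatment open-label challenge or at the End of Treatment double-blind challenge within 30 days of last dose | Not an AEI | In | Out, including the row for serious events | In |
| Not serious, same occasions | Not an AEI | Out | Out | In |
| Serious, at the Study Exit challenge | Not an AEI | Out (not treatment-emergent) | Out | In |

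Only the first line shows a conflict, so the problem is confined to serious reactions inside the window.

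The next question is which statement is out of step. Protocol 8.1.4, the opening of SAP 9.2, SAP 9.1 and SAP 9.2.1 all exclude challenge reactions without exception. The epinephrine item in the same sentence of SAP 9.2 also excludes challenges without exception. The clause for serious anaphylaxis stands alone.

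A reconciling reading can be tried. The AEI summary is limited to treatment-emergent AEIs. If that term carries the 9.2.1 definition, the event in the first line leaves both summaries and the counts agree. The exception for serious reactions then has no effect. So the text either gives two rules or contains a clause that does nothing, and no section says which is meant.

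Last, what would be lost by deleting the clause. SAP 9.1 and 9.2.1 already keep challenge reactions out of their summaries. SAP 10.2 only lists maximum symptom severity at each challenge. SAP 9.12 summarizes rescue medication at challenges, but not reactions or their seriousness. The clause may therefore be the only route by which serious challenge anaphylaxis reaches a summary of adverse events.

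**The case against.** The strongest reply is that the effect is small and leaves the primary endpoint alone. Much of this stands.

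- The anaphylaxis endpoint has its own section, 9.2.1, and its rule is unambiguous. A reader might infer that the reported frequency of anaphylaxis is distorted. The documents do not support that: the stray clause belongs to a different output.
- A reader might infer that a procedure risk would be attributed to AR101. The documents say otherwise. Protocol 8.3 makes serious challenge reactions procedure-related, protocol 8.1.4 and SAP 9.2 say challenge reactions are not considered related to study product, and SAP 9.2 keeps treatment-related events as separate categories.
- The counts need not differ. A difference requires at least one serious anaphylactic reaction at a challenge in the window, and the documents report none for ARC008. The 9.2 item can also be read as a composite of epinephrine use and anaphylaxis, which would not be directly comparable with the 9.2.1 count.
- No data are lost, because all episodes are listed.

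None of this removes the contradiction between the two paragraphs of SAP 9.2, or the different rule in 9.2.1.

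**Conclusion.** The inconsistency is real and minor. SAP 9.2 contradicts itself and protocol 8.1.4, and its second paragraph applies a different rule from SAP 9.2.1. The two summaries can count a serious anaphylactic reaction differently if it occurs at an open-label challenge, or at the End of Treatment double-blind challenge, within 30 days of last dose. This assumes that the AEI clause is applied as written; if it is overridden by the 9.2.1 definition, the counts agree and the clause is dead text.

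The size cannot be given, because the documents do not state how many such reactions occurred or are expected. It is tempting to take the 2 serious events among severe anaphylaxis in protocol 1.4.1.1 as a base and say that one more event would raise the count by half, since (2 + 1)/2 = 1.5. That is not a statement about this trial. The 2 are program-wide to 31 July 2020, among 1237 treated subjects, and cover only anaphylaxis graded severe, while the added event is an assumption.

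**What to change.** Apply one rule for challenge reactions in SAP 9.1, 9.2 and 9.2.1. Two changes should be made together:

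1. Remove the exception for serious reactions from the AEI listing and summary in SAP 9.2, so that they agree with the section's own opening, SAP 9.2.1 and protocol 8.1.4.
2. Report serious allergic reactions at food challenges in a separate row or small table, labelled procedure-related in line with protocol 8.3. Epinephrine use need not be repeated there, since SAP 9.12 already summarizes rescue medication at challenges.

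The first change without the second could leave these events in listings only.

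SAP 1.1 says that Version 2 was made after database lock and is restricted to Appendix A, and SAP 6.1 expects amendments to the planned analysis before lock. If the text can no longer change, state the rule actually applied in a footnote to both tables and in the clinical study report, where protocol section 9 already requires deviations from the SAP to be described. The cost is a phrase or footnote and one small extra table.
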